9.2 Secondary Efficacy Analysis

The two key secondary efficacy parameters are:

[figure not shown]
- Change from baseline in MADRS total score at 28 days after first dose of treatment
- Change from baseline in S-STS total score at 28 days after first dose of treatment

Analysis of change from baseline in MADRS total scores and change from baseline in S-STS total score will be performed using mixed-effects model for repeated measures (MMRM) with terms for treatment, study center, visit, baseline, and treatment-by-visit and baseline-by-visit interactions. An unstructured covariance matrix will be used to model the covariance of within-patient scores. The Kenward-Roger approximation will be used to estimate denominator degrees of freedom (Kenward et al, 1997). The treatment difference for rapastinel versus placebo at selected timepoints will be estimated and reported along with the corresponding 95% CI and the p-value for superiority testing.

In the case that the MMRM with unstructured covariance fails to converge with the default algorithm, then the Fisher scoring algorithm will be used to provide better initial values of the covariance parameters; if the model still does not converge, a simplified model without term for study center will be used to find the initial values of the covariance parameters. In the rare event that model still does not converge after using those initial values, simplified covariance structures will be used to fit the model in the following order: (1) ante-dependence, (2) heterogeneous autoregressive, (3) Toeplitz, and (4) compound symmetry. If MMRM still fails to converge, by visit ANCOVA model similar to the primary efficacy analysis will be used for the analysis.

Let H1 and H2 represent the treatment effect comparisons of rapastinel with placebo in regards to the primary efficacy parameters of change from baseline in MADRS total score and change from baseline in S-STS total score at 1 day after first dose of treatment, respectively; and let H3 and H4 represent the treatment effect comparisons of rapastinel with placebo in regards to the secondary efficacy parameters of change from baseline in MADRS total score and change from baseline in S-STS total score at 28 days after first dose of treatment. The graphical procedure displayed in [Figure 9.2-1](#) will be employed to control the overall familywise error rate at $\alpha=0.049$.

Figure 9.2-1. Graphical Testing Procedure

Specifically, H1 and H2 will be tested at $\alpha=0.0245$ separately. If H1 is rejected, H3 will then be tested at $\alpha=0.0245$. If H2 is rejected, H4 will then be tested at $\alpha=0.0245$. If H3 is rejected but H2 is not rejected, H2 will be further tested at $\alpha=0.049$. If H2 is rejected at $\alpha=0.049$, H4 will be further tested at $\alpha=0.049$. Similarly, if H4 is rejected but H1 is not rejected, H1 will be further tested at $\alpha=0.049$. If H1 is rejected at $\alpha=0.049$, H3 will be further tested at $\alpha=0.049$.

[REDACTED]

[REDACTED]

[REDACTED]

[figure not shown]
[REDACTED]

[REDACTED]

[REDACTED]

[REDACTED]

[REDACTED]

[REDACTED]

[REDACTED]

[REDACTED]

[REDACTED]

[REDACTED]

[REDACTED]

[REDACTED]

[REDACTED]

[REDACTED]

[REDACTED]

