Consent and screening procedures are to be conducted in an inpatient setting for suicidality (see Inclusion Criterion #3). After providing written consent, patients will enter a screening period of no more than 5 days. Every effort should be made to conduct all procedures as early as possible in the Screening. Patients will not receive any investigational product (IP) during the screening period. Treatment for suicidality should proceed per local SOC with limited restrictions ([Section 9.4.9.1](#)).

Efforts should be made to minimize the length of the Screening Period and proceed to randomization or screen failure as rapidly as clinically reasonable. Patients meeting the eligibility criteria at Assessment/Visit 2 (Baseline) will be assigned a treatment by the interactive web response system (IWRS) and enter the DBTP.

9.1.2 **Double-blind Treatment Period**

Patients will be randomized in a ratio of 1:1 to 1 of 2 treatment groups: rapastinel 450 mg IV weekly injection or placebo IV weekly injection. During participation in the study, patients may be treated per local SOC with limited restrictions (see [Section 9.4.9.1](#)) and IP will be administered in addition to SOC treatments.

Naurex

There will be 4 study visits during the first week of the DBTP:

- Visit 2: Baseline IP dosing

Note: If Baseline is ≤ 1 day since Screening assessments were conducted, specified Baseline assessments do not need to be repeated and Screening assessments will count as Baseline (see Section 9.5.5.2 for details).

- Visit 3: 4 hours following the baseline IP dosing
- Visit 4: 1 day following the baseline IP dosing
- Visit 5: 4 days following the baseline IP dosing

There will be 2 study visits during the second week of the DBTP:

- Visit 6: 7 days following Visit 2
- Visit 7: 1 day following Visit 6

There will be 3 weekly study visits during the remainder of the DBTP:

- Visit 8: 14 days following Visit 2
- Visit 9: 21 days following Visit 2
- Visit 10: 28 days following Visit 2

If necessary, study visits may be conducted up to 2 days before or after the scheduled visits except for Assessment/Visit 3 (which must be conducted approximately 4 hours after Visit 2), Visit 4 (which must be conducted 1 day after Visit 2), and Visit 7 (which must be conducted 1 day after Visit 6). All patients who receive IP must complete Visit 10 or Early Termination (ET) Visit.

[figure not shown]

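### If both the unstructured and the ante-dependence fits fail, the remaining SAP 9.2 fallback structures can give the Day 28 tests of H3 and H4 a wrong error rate (minor)

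*SAP*

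**What the plan says.** SAP 9.2 analyses change from baseline in MADRS and S-STS at Day 28 by MMRM. For the main fit, "An unstructured covariance matrix will be used to model the covariance of within-patient scores", and "The Kenward-Roger approximation will be used to estimate denominator degrees of freedom".

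If that fit does not converge, the SAP tries Fisher scoring for starting values, then starting values from a model without study center. Only after that: "In the rare event that model still does not converge after using those initial values, simplified covariance structures will be used". Ante-dependence is first in the order, which then continues "2) heterogeneous autoregressive, (3) Toeplitz, and (4) compound symmetry". The last resort is: "If MMRM still fails to converge, by visit ANCOVA model similar to the primary efficacy analysis will be used for the analysis".

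The visible text mentions no empirical (sandwich) standard error at any step. Steps 3 and 4 are named without the word heterogeneous, which step 2 carries.

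Protocol 9.1.2 and SAP Table 13.2-1 put the post-dose visits at 4 hours and Days 1, 4, 7, 8, 14, 21 and 28. One late gap is a single day ("Visit 7: 1 day following Visit 6"), while the last three gaps are six to seven days. Protocol 9.2 says efficacy is assessed at every visit.

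H3 is tested at 0.0245 once H1 is rejected, and H4 likewise after H2. Each can feed back to the other primary endpoint: "If H3 is rejected but H2 is not rejected, H2 will be further tested at" 0.049, and symmetrically for H4 and H1.

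**The concern.** Three of the four fallback structures impose constraints that this visit schedule need not satisfy.

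- **Heterogeneous autoregressive:** has a variance for each visit, but one correlation for every adjacent pair. Days 7 and 8 are treated like Days 21 and 28.
- **Toeplitz:** makes correlation depend on visit order and, read as equal-variance, imposes one variance from 4 hours to Day 28.
- **Compound symmetry:** imposes one variance and one correlation. It makes no assumption about spacing.

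If the constraint is wrong, the model-based standard error at Day 28 is wrong. Kenward-Roger adjusts for small samples on the premise that the structure is right. A variance for each visit does not protect the autoregressive step, because forcing one adjacent correlation also distorts the fitted Day 28 variance.

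H3 and H4 belong to the graph meant to hold familywise error at 0.049. An inflated Day 28 test matters when a Day 1 effect is real and the Day 28 effect is null, which is plausible for a drug studied for rapid action.

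**Working it through.** **The plan's own figures.** SAP 11.0 gives 150 per arm, MADRS difference 3.76 with SD 10, S-STS difference 4 with SD 11, at two-sided 0.049. Power = Φ(difference / (SD × √(2/150)) − z). This gives 0.901 and 0.881, matching the stated 90% and 88%. These are Day 1 figures. The documents state no power or error rate for Day 28.

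**Assumptions not in the documents.** Residual SD 10 at the first post-dose visit, moving to 8, 10, 12 or 14 at Day 28; correlations that decay with time; scores at all eight visits; dropout of 0% or, where stated, 25% completely at random; unqualified Toeplitz and compound symmetry read as equal-variance.

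**Formula.** True level = 2 × Φ(−2.249 × r), where r is the model-based Day 28 SE divided by the true SE, and 2.249 is the two-sided critical value at 0.0245.

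**Compound symmetry, complete data.** The fitted common variance is the mean of the eight visit variances, so r = √(mean variance) / SD at Day 28.

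- SD 10 to 12, linear in time: variances 100.2, 101.4, 105.8, 110.2, 111.8, 121.0, 132.2, 144.0; mean 115.84; r = 10.763/12 = 0.897; level 0.044.
- SD 10 to 12, linear in visit order: mean 121.43; r = 11.019/12 = 0.918; level 0.039.
- SD 10 to 14, linear in time: mean 133.66; r = 11.561/14 = 0.826; level 0.063. In visit order: mean 145.71; r = 0.862; level 0.052.
- SD 10 to 8, linear in time: mean 86.14; r = 9.281/8 = 1.160; level 0.009.
- SD constant: r = 1; level 0.0245.

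**Toeplitz** (best-fitting parameters found numerically, SD linear in time, complete data): 0.0245 for constant SD despite the unequal spacing, 0.043 for 10 to 12, 0.061 for 10 to 14, 0.009 for 10 to 8.

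**Heterogeneous autoregressive** (same method, SD constant at 10). One example has a true correlation of 0.84 between Days 7 and 8 and 0.58 between Days 21 and 28. The single fitted correlation is 0.72, r = 1.118 and the level is 0.012. The main range is about 0.01 to 0.017. Over all shapes tried it ran from 0.005 (no measurement-error component) to 0.0245 (correlations that fit the structure), and it was never inflated.

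**Ante-dependence:** 0.0228 to 0.0245 in every scenario.

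**Dropout of 25%.** Compound symmetry gave 0.0245 to 0.037 with constant SD and up to 0.080 for SD 10 to 14. Toeplitz reached 0.068.

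**Finite-sample check, 150 per arm, complete data.** Compound symmetry with SD 10 to 12 gave 0.048 in 3,000 runs. Heterogeneous autoregressive with constant SD gave 0.017 in 1,500 runs.

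**Power cost of the autoregressive step.** At 0.0245 the Day 1 MADRS assumptions give 84% power; this is borrowed as an illustration only. True levels of 0.017 and 0.010 correspond to critical values of 2.387 and 2.576 in place of 2.249. Power becomes Φ(2.249 + 0.994 − 2.387) = 80% and Φ(2.249 + 0.994 − 2.576) = 75%.

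**Effect on the graph, once this branch is reached.** Suppose H1 is truly false and always rejected, H2 and H3 are null, and their tests are independent.

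- Chance of at least one false rejection among H2 and H3: 1 − 0.9755² = 0.048 if H3 runs at 0.0245; 1 − 0.956 × 0.9755 = 0.067 if it runs at 0.044.
- False rejection of H2 itself: 0.0245 + (level of H3) × 0.0245. This is 0.0251 at 0.0245 and 0.0256 at 0.044, a rise of about 0.0005.

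**The case against.** The strongest objection is remoteness. Three convergence attempts on the unstructured model must fail, then ante-dependence must fail before the autoregressive step, and that step must also fail before Toeplitz or compound symmetry. Only those last two inflate error. This stands, and it is why the point is minor.

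A reader might infer several stronger claims that the documents do not support:

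- **That failure of the unstructured fit alone puts the Day 28 tests at the wrong level.** It does not. Ante-dependence comes first and forces neither equal spacing nor equal variances. The closing by-visit ANCOVA forces neither.
- **That unequal spacing inflates the error.** It did not in any scenario with constant SD and complete data. The autoregressive step became conservative or stayed nominal, and Toeplitz stayed nominal. With complete data, inflation needs the common-variance constraint together with an SD that rises over time.
- **That the Day 1 claims are at material risk.** Under the global null, H1 and H2 gate H3 and H4, so a wrong Day 28 level adds no familywise error. H2 is tested by the Day 1 ANCOVA, which this fallback does not touch, and never above 0.049.
- **That a known Day 28 power is lost.** The 84% is the Day 1 MADRS figure at 0.0245. The SAP states no Day 28 effect size.

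It is also fair to say that the direction and size of any error depend on quantities that the documents do not give.

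**Conclusion.** The gap is real but conditional and minor. If the unstructured and ante-dependence fits both fail, H3 and H4 rest on structures whose model-based inference can be wrong, in either direction. At nominal 0.0245:

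- **Heterogeneous autoregressive:** about 0.01 to 0.017 under correlations that decay with time, with some loss of power.
- **Toeplitz and compound symmetry:** nominal with constant SD and complete data; about 0.009 to 0.015 if the SD falls from 10 to 8; about 0.04 to 0.05 if it rises to 12; about 0.05 to 0.06 if it rises to 14, and higher with substantial dropout.

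These ranges rest on assumed SD profiles, correlations and dropout, and on reading the unqualified structure names as equal-variance. The consequence is mainly for the Day 28 claims when a Day 1 effect is real and the Day 28 effect is not.

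**What to change.** Add one sentence to SAP 9.2: whenever a covariance structure other than unstructured is used, standard errors, confidence intervals and tests of the treatment contrasts will use the empirical (sandwich) estimator clustered by patient, with a named degrees-of-freedom method (for example between-within) in place of Kenward-Roger. The order of structures can stay.

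In a check with 300 patients, Day 28 SD 12, 15% dropout and 677 runs, this moved the level from 0.013 (heterogeneous autoregressive) and 0.044 (compound symmetry) to 0.022 for both, with Monte Carlo error about 0.006.

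The cost is one sentence and one software option. The Kenward-Roger small-sample adjustment is lost in the fallback, which matters little with about 300 patients. The sandwich corrects the standard error only; it does not remove bias in the estimate when dropout depends on earlier scores and the covariance is wrong. Going from ante-dependence straight to the by-visit ANCOVA already in the SAP would also avoid the affected structures, but that analysis uses only patients observed at Day 28. Either choice should be fixed before unblinding, so that it is not made after a convergence failure has been seen.

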10.1 Adverse Events

Adverse events will be coded by system organ class and preferred term using the *Medical Dictionary for Regulatory Activities* and reported separately for DBTP and Safety Follow-up (SFU).

An AE (classified by preferred term) will be considered a treatment-emergent adverse event (TEAE) if it was not present before the first dose of DB IP or was present before the date of the first dose of DB IP and increased in severity after the first dose of DB IP. An AE that becomes serious after the date of the first dose of DB IP will also be considered as TEAE. If more than 1 AE was reported before the first dose of DB IP and coded to the same preferred term, the AE with the greatest severity will be used for comparison with the AEs occurring during each study period analyzed. An AE that occurred more than 30 days after the date of the last dose of DB IP will not be considered as a TEAE.

[figure not shown]
The number and percentage of patients reporting TEAEs and TEAEs leading to study discontinuation in each treatment group will be tabulated by system organ class and preferred term and further categorized by severity and causal relationship to the IP. If more than 1 AE is coded to the same preferred term for the same patient, the patient will be counted only once for that preferred term using the greatest severity and strictest causality for the summarization by severity and causal relationship.

The incidence of common ($\geq 2\%$ of patients in any treatment group) TEAEs will be summarized by preferred term and treatment group and sorted by decreasing frequency for the test treatment.

A serious adverse event (SAE) that occurred between the date of the first dose of DB IP and 30 days after the date of the last dose of DB IP, inclusive, will be considered a treatment-emergent SAE (TESAE). The number and percentage of patients who have TESAEs will be summarized by preferred term and treatment group.

Listings will be presented for patients with SAEs, patients with AEs leading to discontinuation, and patients who die (if any). All patients with SAEs, including SAEs reported during the screening period and the SFU, and patients discontinuing because of AEs occurring before the start of IP will be included in these listings.

[REDACTED]	[REDACTED]	[REDACTED]	[REDACTED]	[REDACTED]
[REDACTED]	[REDACTED]	[REDACTED]	[REDACTED]	[REDACTED]
[REDACTED]	[REDACTED]	[REDACTED]	[REDACTED]	[REDACTED]
[REDACTED]	[REDACTED]	[REDACTED]	[REDACTED]	[REDACTED]
[REDACTED]	[REDACTED]	[REDACTED]	[REDACTED]	[REDACTED]
[REDACTED]	[REDACTED]	[REDACTED]	[REDACTED]	[REDACTED]
[REDACTED]	[REDACTED]	[REDACTED]	[REDACTED]	[REDACTED]
[REDACTED]	[REDACTED]	[REDACTED]	[REDACTED]	[REDACTED]

[REDACTED]

[REDACTED]

[REDACTED]

[REDACTED]

[Redacted]

[Redacted]

[Redacted]

[Redacted]

[Redacted]

[Redacted]

[Redacted]

[Redacted]

[Redacted]

[Redacted]

[Redacted]

10.6 Interim Analysis

An unblinded interim analysis will be conducted to identify early signs of futility. An internal, but separate, fire-walled Statistical Analysis Group and Data Review Committee will be established to conduct the unblinded interim analysis, review the unblinded results and make recommendations regarding the continuation of the study. To maintain the scientific reliability of statistical analyses after the final database lock, preserve the integrity of study conduct, and guard from introducing any potential bias into the conduct of the study and/or analysis of its results, individuals in these two groups will not be involved in any operational aspects of the trial. Additionally, to adjust for multiple comparison issues caused by having several looks at the data, the Bonferroni method will be applied to split the overall Type I Error between the interim and final analysis ($\alpha = 0.001$ and 0.049 2-sided, respectively) to further protect the integrity of the study. Further details of the unblinded interim analysis, in particular its scope, the processes put in place to maintain study validity, team structures, and responsibilities, are documented within a separate Data Review Committee Charter.

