11.0 DETERMINATION OF SAMPLE SIZE

This study will randomize approximately 300 patients to the rapastinel 450 mg and placebo groups in a 1:1 ratio. The sample size is determined based on the primary efficacy endpoint of the change from baseline in the MADRS total score at 1 day after the first dose of treatment. Assuming the SD of the change from baseline in the MADRS total score is 10 points, a sample size of 150 patients per treatment group will provide about 90% power to detect a difference of 3.76 points for a rapastinel dose versus placebo at a 2-sided significance level of 4.9%.

With respect to S-STS total score, 150 patients per arm will provide approximately 88% power for a treatment difference of 4 between rapastinel 450 mg and placebo and estimated standard deviation of 11 based on the blinded analysis in April 2019 at a 2-sided significance level of 4.9%.

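### SAP 10.6 sets aside 0.001 of alpha for a look described only as futility, where none is needed, and the power in SAP 11.0 leaves that look out

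*SAP*

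**What the plan says.** SAP 10.6 gives the interim one purpose: "An unblinded interim analysis will be conducted to identify early signs of futility". It then adds an alpha adjustment, under which "the Bonferroni method will be applied to split the overall Type I Error between the interim and final analysis". The shares are 0.001 two-sided at the interim and 0.049 at the end, and the reason offered is "to adjust for multiple comparison issues caused by having several looks at the data". It describes no efficacy boundary and no early claim of benefit. It also gives no futility boundary, timing, endpoint or binding status; further details "are documented within a separate Data Review Committee Charter". The committee makes recommendations on whether the study continues.

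The 0.049 carries into SAP 9.2, where the graph starts each primary endpoint at 0.0245 and can recycle up to 0.049.

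SAP 11.0 states, for MADRS, that "a sample size of 150 patients per treatment group will provide about 90% power to detect a difference of 3.76 points" with SD 10. For S-STS it gives approximately 88% for a difference of 4 with SD 11. Both are at two-sided 4.9%, and the section does not mention the interim.

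Protocol 9.7.8 says that no interim analysis is planned, while SAP 14.0 declares no changes from protocol Amendment 2. The text supplied does not show whether the protocol in hand is that amendment, so this is a separate item to reconcile.

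**The concern.** A futility look and an efficacy look affect different errors. Stopping for futility means not rejecting, so it can only lower the type I error; what it raises is the type II error. SAP 10.6 adjusts the first. SAP 11.0 is silent on the second.

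Two things are at stake. Every final threshold (0.0245 and 0.049) is slightly stricter than a futility-only look requires. And a reader of SAP 11.0 cannot tell whether the stated power is close to the power of the design as it will be run, or several points too high.

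**Working it through.** **Inputs.** From SAP 11.0: n = 150 per arm; MADRS difference 3.76, SD 10; S-STS difference 4, SD 11; alpha 0.049 two-sided. From SAP 10.6: 0.001 and 0.049. From SAP 9.2: 0.0245 per primary at the first step. The futility rule and the information fraction t are not given, so those below are assumptions.

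**Step 1: reproduce the stated power.** The drift is θ = (difference/SD) × √(n/2).
- MADRS: 0.376 × √75 = 3.256
- S-STS: (4/11) × √75 = 3.149

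The critical value at 0.049 two-sided is c = 1.969. The normal approximation gives Φ(3.256 − 1.969) = 90.1% and Φ(3.149 − 1.969) = 88.1%. Noncentral t with 298 df gives 89.9% and 87.9%. Both match SAP 11.0, so the stated powers assume that every trial runs to 150 per arm.

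**Step 2: cost of the 0.001** (noncentral t, n = 150 per arm).

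| Endpoint | 0.049 → 0.05 | 0.0245 → 0.025 |
|---|---|---|
| MADRS | 89.92% → 90.07% (+0.15) | 83.97% → 84.16% (+0.19) |
| S-STS | 87.91% → 88.08% (+0.17) | 81.24% → 81.45% (+0.21) |

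**Step 3: effect of a futility stop on power.** Let Z1 ~ N(θ√t, 1) be the interim statistic and Z2 ~ N(θ, 1) the final one, with correlation √t. If the trial stops when Z1 < b, the power loss is P(Z1 < b and Z2 ≥ c). For conditional power below p, with z_p the normal quantile:
- current trend: b = √t × (c + √(1−t) × z_p)
- design effect: b = (c + √(1−t) × z_p − θ(1−t)) / √t

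Example: current trend, p = 0.20, t = 1/2. Then b = 0.707 × (1.969 − 0.707 × 0.842) = 0.97. MADRS power falls from 90.1% to 85.4% and S-STS power from 88.1% to 83.1%.

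Loss in percentage points for one endpoint at alpha 0.049, assuming the stop is always followed:

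| Assumed rule | t | MADRS | S-STS |
|---|---|---|---|
| Current trend, below 10-30% | 1/3 | 5.5-11.1 | 5.8-11.5 |
| Current trend, below 10-30% | 1/2 | 2.7-6.8 | 2.9-7.2 |
| Current trend, below 10-30% | 2/3 | 1.3-4.0 | 1.5-4.4 |
| Design effect, below 10-30% | 1/3 to 2/3 | at most 0.43 | at most 0.57 |
| Z < 0 | 1/2 | 0.23 | 0.25 |

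**Step 4: effect on type I error.** Set θ = 0 in the same formula. With the 20% current-trend rule at half information, one-sided error falls from 2.45% to 2.01%. With the final test at 0.05 and the assumed MADRS rules, it lies between 1.77% and 2.50%. It never exceeds the nominal level.

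**Step 5: if 0.001 is really an efficacy boundary.** Testing at 0.001 and then at 0.049 gives an overall two-sided error of 0.0495, 0.0492 and 0.0491 at t = 1/3, 1/2 and 2/3. The final level that uses exactly 0.05 is 0.04949, 0.04978 and 0.04996 at t = 0.3, 0.5 and 0.7.

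**The case against.** The split is valid, it costs at most about 0.2 points, and SAP 10.6 gives a reason for it: protecting the integrity of a study in which groups internal to the sponsor see unblinded data. The look's scope is in a charter that is not available here, and if that charter lets an efficacy result be acted on, the 0.001 has a use. Raising alpha around an unblinded look that may already have taken place would be a poor trade for so small a gain. All of this stands, and it limits the remedy.

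On power, the loss depends on an unseen rule, and lenient rules leave the rounded statements true: with Z<0 at half information the figures are 89.9% and 87.9%. The largest losses need a 30% current-trend rule at one third of the information, which would stop about 16% of trials in which the MADRS design effect is true. The calculation also assumes automatic stopping, whereas SAP 10.6 speaks of recommendations, and a rule requiring both endpoints to look futile would cost less. Finally, the losses are computed at 0.049, whereas the first tests run at 0.0245. There the 20% current-trend rule at half information costs S-STS 5.8 points (81.6% to 75.8%, normal approximation) instead of 5.0. These are fair limits on the size. They do not answer the point that SAP 11.0 makes no allowance for the look.

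A reader might go further and infer that the look endangers the type I error, that the 0.001 certainly protects nothing, or that the stated power is materially too high under any charter rule. The documents support none of these. The error is controlled with room to spare, the charter might give the 0.001 a purpose, and some plausible rules cost almost nothing.

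**Conclusion.** The point holds in a limited form. As SAP 10.6 is written, the look is for futility only and the alpha split is conservative and unnecessary; this affects clarity and 0.15 to 0.2 points of power, not validity. SAP 11.0 reports fixed-sample power. For one endpoint at 0.049, the overstatement ranges from near 0 to about 11.5 points over the assumed rules, and the documents do not show where in that range the trial lies. The size rests on three assumptions: the rule, its timing, and that a recommended stop is followed. The power at the first-step level of 0.0245 (about 84% for MADRS and 81% for S-STS) is a larger shortfall against the stated figures that does not depend on the look. It is a separate matter, but the restated power should use the alpha of the graph.

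**What to change.** In SAP 10.6, state whether the look can lead only to a futility stop, and give the rule, its timing, the endpoint or endpoints it uses, and whether it is binding. Then settle the 0.001:

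- Futility-only, and no unblinded look has yet taken place: drop the split and run the SAP 9.2 graph at 0.05 (0.025 per primary, 0.05 after recycling).
- Futility-only, but the look has already occurred: keep 0.049 and describe it as a conservative reserve.
- An efficacy claim at 0.001 is possible: say so, and replace 0.049 with the exact two-look final level for the actual information fraction (about 0.0495 to 0.0500).

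In SAP 11.0, restate the power of both primary endpoints with the futility rule included, at the alpha levels that the graph actually uses.

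The cost is SAP wording and one power calculation, with no added patients or procedures. The downside is that the stated power may become slightly less favourable.
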